8.5. Data and Safety Monitoring Plan

The proposed study will conform to rigorous standard monitoring procedures, standardized reporting of adverse events (Adverse Event Report Forms are completed by study coordinators and sent immediately to the investigators), and regular review of the study by a Data and Safety Monitoring Board (DSMB). The PI has primary responsibility for the overall conduct of the study, including the safety of human subjects. The PI will ensure appropriate (1) conduct of the informed consent process (e.g. that informed consent is obtained before proceeding with study procedures); (2) enrollment of study subjects; (3) collection and analysis of data; (4) implementation of study procedures to ensure consistent monitoring of subjects for possible adverse events; (5) review of adverse events and reporting to the DSMB and the IRBs; and (6) maintenance of the privacy and confidentiality of study subjects. The PI maintains ultimate responsibility for the project and for the safety of study participants. The PI will be in contact with the research team on a regular basis to review the progress of the study and address any human subject issues that occur. These discussions may involve adverse event prevention

measures, recruiting of appropriate study subjects, research staff training on protection of human subjects, as well as occurrence of adverse events, unexpected incidents, or protocol problems.

8.5.1. Data and Safety Monitoring Board

A DSMB will be established by the study team in cooperation with the sponsor to assess at intervals the progress of a clinical trial, safety data, and critical efficacy variables and recommend to the sponsor whether to continue, modify or terminate a trial. The DSMB will have written operating procedures and maintain records of all its meetings, including interim results; these will be available for review when the trial is complete. The DSMB will be a separate entity from the US and host-country Institutional Review Boards (IRBs). The independence of the DSMB is intended to control the sharing of important comparative information and to protect the integrity of the clinical trial from adverse impact resulting from access to trial information. DSMB members will not participate in the study as investigators and will not have conflicts of interest regarding the study or the investigational product. The composition of the DSMB will include at minimum:

DSMB Chair, having experience and expertise in clinical trials
Scientist with expertise in malaria.
Scientist with expertise in pharmacology
Biostatistician with expertise in clinical trials.

A member of the sponsor, NICHD, will be invited to attend and thus have access to unblinded information, and control of dissemination of interim trial results within the sponsor organization. The DSMB will meet at least annually to review progress of the clinical trial and safety data.

The DSMB will review the study for progress and safety. The PI will provide information that will allow the DSMB to review and assess the following:

- The research protocol, informed consent documents and plans for data safety and monitoring;
- Periodic assessments of data quality and timeliness, participant recruitment, accrual and retention, participant risk versus benefit, and other factors that can affect study outcome;
- Factors external to the study when relevant information, such as scientific or therapeutic developments, may have an impact on the safety of the participants or the ethics of the trial;

- Study performance to make recommendations and assist in the resolution of problems;
- The safety of the study participants;
- The safety and scientific progress of the trial;
- The continuation, termination or other modifications of the trial based on the observed beneficial or adverse effects of the treatment under study;
- The confidentiality of the data and the results of monitoring; and
- Any problems with study conduct, enrollment, sample size and/or data collection.

The first meeting of the DSMB will take place prior to the initiation of the study to discuss the protocol and the Data Safety Monitoring Plan. Meetings of the DSMB shall be held according to the plan outlined above. Meetings shall be closed to the public because discussions may address confidential patient data. Meetings may be convened as conference calls as well as in person. An emergency meeting of the Board may be called at any time should questions of patient safety arise. The DSMB may request the presence of study investigators at such meetings.

The study PI will distribute study information to the DSMB at least 10 days prior to a scheduled meeting. The DSMB may request additions and other modifications to this information on a one-time or continuing basis. This information will consist of two parts: (1) information on study progress such as accrual, baseline characteristics, and other general information on study status and (2) any confidential data on study outcomes, including safety data. A formal report from the DSMB should be supplied to the PI within 6 weeks of each meeting. Each report should conclude with a recommendation to continue or to terminate the study. This recommendation should be made by formal majority vote. A recommendation to terminate the study should be transmitted to the PI, IRBs and NIH as rapidly as possible, by immediate telephone and fax if sufficiently urgent. In the event of a split vote in favor of continuation, a minority report should be contained within the regular DSMB report.

8.5.2. Interim safety analysis

Over the course of the trial, we will perform an interim safety analysis in addition to a final safety analysis for a total of two sequential evaluations of study safety. Safety will be evaluated separately for pregnant women and infants evaluating the incidence rate ratio of significant adverse events (grade 3/4 & SAEs). The interim safety analysis for pregnant women will be performed when ½ of the study subjects have given birth and for infants 0-24 months of age when ½ of the anticipated total observation time has been accrued. A separate standardized

test statistic will be calculated for the adverse event incidence rate ratio for pregnant women and infants. If this statistic exceeds the nominal critical value calculated using the error spending function (Table 11), then a statistically significant result will have been achieved at the time of that analysis. In that event, the sponsor will be notified and a report submitted for review by the Data Safety Monitoring Board (DSMB). In each interim safety analysis, the study team will present information on recruitment and the results of interim safety analyses to the DSMB, which will review the data and recommend a course of action.

Table 11. Schedule of interim safety analysis and boundaries to monitor study outcome

Number of Evaluable Subjects Accrued or % of Total Accrual Time	Test Statistic		Alpha	Cumulative Alpha
	Lower Bound	Upper Bound		
N=150 or 50% of accrual time	-2.51	2.51	0.00601	0.01210
N=300 or 100% of accrual time	-1.99	1.99	0.02313	0.05000

This analysis assumes $\alpha=0.05$ (two-sided test), O’Brien-Fleming boundaries (DeMets error-spending function) and 300 trial participants. We will utilize Programs for Computing Group Sequential Boundaries Using the Lan-DeMets Method.

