3. STUDY DESIGN

This will be a double-blinded randomized controlled phase III trial of 300 HIV uninfected pregnant women and the children born to them. The study interventions will be divided into two phases. In the first phase, HIV uninfected women at 12-20 weeks gestation will be randomized in equal proportions to one of three IPTp treatment arms: 1) 3 doses of SP, 2) 3 doses of DP, or 3) monthly DP. All three interventions arms will have either SP or DP placebo to ensure adequate blinding is achieved in the study as outlined in appendix D. Follow-up for the pregnant women will end approximately 6 weeks after giving birth. In the second phase of the study, all children born to mothers enrolled in the study will be followed from birth until they reach 36 months of age. Children born to mothers randomized to receive 3 doses of SP during

pregnancy will receive DP every 3 months between 2-24 months of age. Children born to mothers randomized to receive 3 doses of DP or monthly DP during pregnancy will receive either DP every 3 months or monthly DP between 2-24 months of age. To ensure adequate blinding, children who will receive DP every 3 months will be given DP placebo during the months they will not be taking DP. Children will then be followed an additional year between 24-36 months of age following the interventions.

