5. STUDY TREATMENT

5.1. Treatment Group Assignments

There will be 5 treatment arms which include both the intervention for the woman during pregnancy and her unborn child(ren) during infancy (Table 3). Non-singleton births from the same mother will be assigned to the same intervention. We will use a 2:1:1:1:1 randomization scheme targeting 100, 50, 50, 50, 50 pregnant women in treatment arms A-E respectively. A randomization list will be computer generated by a member of the project who will not be directly involved in the conduct of the study. The randomization list will include consecutive treatment numbers with corresponding random treatment assignments. Randomized codes will correspond to the 5 treatment groups using permuted variable sized blocks of 6 and 12 (to account for treatment group A being represented twice as often as the other 4 treatment groups). Sealed copies of the original randomization list and documentation of the procedure used to generate the lists will be stored in the project administrative offices in San Francisco and Kampala. Prior to the onset of the study, a set of sequentially numbered, opaque, sealed envelopes will be prepared. Each envelope will be marked on the outside with the treatment allocation number. The inside of the envelope will contain a piece of paper with the treatment allocation number and treatment group assignment along with a piece of carbon paper.

Table 3. Treatment arms with assignment of study drugs during pregnancy and infancy

Phase of intervention	Treatment arm				
	A	B	C	D	E
During pregnancy	3 dose SP	3 dose DP	3 dose DP	Monthly DP	Monthly DP
During infancy	3 monthly DP	3 monthly DP	Monthly DP	3 monthly DP	Monthly DP

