6.12. Management of Adverse Events Potentially Related to Study Drugs

The following section outlines management of adverse events potentially related to study drugs (SP or DP). Given the double blinded nature of the intervention, study clinicians and study participants will not be aware of what study drugs are being administered. Therefore all study participants will be considered potentially exposed to either study drug during the period study drugs are first given up to one month after the last dose of study drug is given.

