8.5.3. Stopping rules

The DSMB will determine whether to stop the study for early evidence of intervention safety problems after a thorough review of interim data. Interim reports will provide cumulative enrollment figures and cumulative adverse birth outcomes, serious adverse events (classified according to grade) for both women and children, sorted by study arm. Brief clinical descriptions of key events will also be provided. The PI will be responsible for immediately reporting to the funding agency any temporary or permanent suspension of the project and the reason for the suspension.

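### Section 8.5 of the protocol routes comparative interim safety data through the PI and the study team of a double-blind trial, and assigns nobody outside study conduct to prepare the closed report

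*Protocol*

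**What the plan says.** **Blinding.** Protocol section 3 states: "This will be a double-blinded randomized controlled phase III trial of 300 HIV uninfected pregnant women and the children born to them". Section 6.12 adds that "study clinicians and study participants will not be aware of what study drugs are being administered", and section 5.4 has the study nurse who gives the drugs blinded as well. Section 8.5.1 explains the DSMB's independence as a means of limiting who sees comparative information and of shielding the trial from the effects of such access.

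**Data route.**
- Section 8.5.2, in the first person plural, makes the interim safety analysis a task of the protocol's authors, and then says that "the study team will present information on recruitment and the results of interim safety analyses to the DSMB". If the statistic crosses its boundary, the sponsor is notified and a report goes to the DSMB.
- Section 8.5.1: "The study PI will distribute study information to the DSMB at least 10 days prior to a scheduled meeting". The second of the package's two parts is "any confidential data on study outcomes, including safety data".
- Section 8.5.3: the interim reports give cumulative enrolment, adverse birth outcomes and "serious adverse events (classified according to grade) for both women and children, sorted by study arm".

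**Allocation.** Section 5.1: "We will use a 2:1:1:1:1 randomization scheme targeting 100, 50, 50, 50, 50 pregnant women in treatment arms A-E respectively". Table 3 shows arm A as the only one with SP. The randomisation list is generated "by a member of the project who will not be directly involved in the conduct of the study".

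**The concern.** In a blinded trial, by-arm interim results are normally kept from those who recruit, treat and assess participants. Here the protocol does not merely leave the reporting line open. It names the PI as distributor of the confidential part and the study team as presenter of the results. It names no independent statistician and no report withheld from the team. DSMB meetings are closed only to the public, and investigators may be asked to attend.

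At the maternal look, half of the planned women have yet to deliver, and the children are followed to 36 months of age. Several data items still to be collected rest on judgement:
- relatedness of adverse events to study drug (section 7.1.2);
- withdrawal at the site investigator's discretion (section 6.9, reasons 4 and 5);
- smears during follow-up of non-malarial illness (section 6.3).

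The smears feed into malaria incidence, the primary outcome for hypotheses 2 and 3. Knowledge of emerging differences could colour these judgements, and a disclosure cannot be reversed.

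**Working it through.** **1. The route, step by step.**

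| Step | Who, according to the protocol | Section |
|---|---|---|
| Perform the interim comparison | the authors, in the first person plural | 8.5.2 |
| Write the by-arm report | not named | 8.5.3 |
| Distribute confidential outcome and safety data | the PI | 8.5.1 |
| Present the results | the study team | 8.5.2 |
| Control onward disclosure | stated for the sponsor's organisation; no rule for the PI or team | 8.5.1 |

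No step is given to a person outside study conduct.

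**2. Would coded arm labels be enough?** The reports show cumulative enrolment, so group sizes may be visible.

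The plan's own figures first. With weights 2:1:1:1:1 (sum 6) and 300 women, arm size = 300 × weight / 6:
- A: 300 × 2/6 = 100;
- B, C, D, E: 300 × 1/6 = 50 each.

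This reproduces section 5.1. At the interim look with N=150:
- A: 150 × 2/6 = 50;
- B, C, D, E: 150 × 1/6 = 25 each.

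The answer then depends on what the reports call an arm:
- *Five arms A to E (section 5.1, Table 3):* 50/25/25/25/25. The double-sized group is A, hence SP.
- *Three pregnancy regimens (section 3, Table 9):* SP 50, three-dose DP 25 + 25 = 50, monthly DP 25 + 25 = 50. Size does not identify SP.
- *Two infant regimens (Appendix D):* 3-monthly DP is A+B+D = 100 + 50 + 50 = 200 by women randomised, and monthly DP is C+E = 50 + 50 = 100. With the infants expected in Table 9 this is 90 + 45 + 45 = 180 against 45 + 45 = 90. Either way the ratio is 2:1.

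**3. Allowing for chance.** The check used 5,000 simulated lists per setting, with blocks of 6 and 12 in random order. Equal block probabilities, and a random subset of the 300 allocations at the look, are assumptions.

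| Grouping | Event counted | 150 of 300 | 60 of 300 (assumed early look) |
|---|---|---|---|
| Arms A to E | A strictly largest | 100% | 94% |
| Three pregnancy regimens | SP strictly largest | 31% | 31% |
| Two infant regimens | 3-monthly group larger | 100% | 99.8% |

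The 31% is close to the one in three that equal groups give, less ties. The infant row uses mothers' allocations as a stand-in, because the infant look is timed by observation time and not by number of children.

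**4. Where bias could enter.** Primary smears are largely rule-driven: fever or reported fever triggers one (section 6.1), and routine visits include one every 4 weeks (section 6.5). Placental histology is read by two experts, with a third for disagreements (section 6.10.3). What remains exposed is the judgement-based items listed above.

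**The case against.** The strongest reply is that no single sentence says that blinded staff see unblinded results. The PI distributes, the study team presents, and the by-arm reports have no named author and no stated treatment labels. The term study team is undefined and could cover people who already know allocations, such as the pharmacist who keeps the master list (section 5.2). Only clinicians, the nurse and participants are named as blinded; the PI and the analyst are not. Section 8.5.1 already separates progress information from confidential data and provides for written DSMB operating procedures, which are not shown and could add a firewall. The planned interim test covers grade 3/4 and serious adverse events, not placental malaria or malaria incidence.

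Much of this stands, and it rules out stronger readings that a reader might infer:
- *That clinicians are certain to be unblinded.* The text does not say so, and knowing which group is SP does not reveal any one participant's allocation.
- *That SP is recognisable by size in any coded report.* This holds for arms A to E, but not for the three equal pregnancy regimens, which section 3 also calls arms.
- *That DSMB procedures could not cure the problem.* They could, although they would have to displace the route that the protocol states.

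The reply does not remove the core. A reader who follows section 8.5 as written puts comparative data in the hands of the PI and team, against the purpose that section 8.5.1 gives for the DSMB's independence.

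**Conclusion.** The point holds as a weakness in a stated rule, not as missing detail: section 8.5 sends comparative interim data through the PI and study team and puts no one outside study conduct in between. Coding alone fails for arms A to E (50 against 25 in each other arm at N=150) and for the infant regimens (2:1). It suffices for the women if they are shown by the three equal regimens.

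The consequence is a possible but limited bias in adverse event relatedness, discretionary withdrawal and some smears. The size of that bias cannot be derived from the protocol. The two-reader histology outcome is not materially exposed, and no test, alpha or sample size is affected. The conclusion assumes that section 8.5 is followed as written and that no unseen DSMB procedure overrides it. It should be fixed, but it does not by itself invalidate the design.

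**What to change.** Amend sections 8.5.1 to 8.5.3 as follows:
- The PI and study team supply only the open report: accrual, data quality and pooled events.
- A designated person with no role in study conduct merges the codes, runs the interim statistic and sends the by-arm closed report, for women and infants, directly to the DSMB. It is withheld from the PI and team. The project member who generated the randomisation list could serve, if qualified; section 5.1 places that person outside conduct but says nothing about statistical skills. The DSMB's own biostatistician is a poor choice, as one person would then both prepare and review the analysis.
- Any boundary crossing reaches the DSMB by the same route.
- As a secondary safeguard, women's data are shown by the three equal pregnancy regimens. This does not help the infant comparison, which stays at 2:1, so the reporting firewall is the essential change.

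The cost is a few sentences in the protocol and a small analysis task for someone outside study conduct. The change should be in place before the first by-arm look.

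### The Table 11 safety boundaries do not belong to the stated two-look O'Brien-Fleming plan; they match looks 2 and 3 of a three-look plan

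*Protocol*

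**What the plan says.** Protocol section 8.5.2 fixes everything needed to compute the boundaries.

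- **Number of looks:** one interim and one final analysis, "for a total of two sequential evaluations of study safety".
- **Interim timing:** for women it is "performed when ½ of the study subjects have given birth"; for infants it is "when ½ of the anticipated total observation time has been accrued".
- **Method:** the note to Table 11 gives alpha 0.05 and specifies "two-sided test), O’Brien-Fleming boundaries (DeMets error-spending function) and 300 trial participants". The software named is "Programs for Computing Group Sequential Boundaries Using the Lan-DeMets Method".

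Table 11 then prints:

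| Row | Bounds | Alpha | Cumulative alpha |
|---|---|---|---|
| "N=150 or 50% of accrual time" | ±2.51 | 0.00601 | 0.01210 |
| "N=300 or 100% of accrual time" | ±1.99 | 0.02313 | 0.05000 |

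A statistic beyond these values counts as statistically significant. The sponsor is then notified and a report goes to the DSMB. The same bounds serve the separate tests in women and in infants.

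**The concern.** O'Brien-Fleming spending is very sparing early on. A bound of 2.51 with 0.0121 already spent is too generous for half the information, so the table and the method written beneath it appear to describe different designs.

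Table 11 is the only numeric trigger in the monitoring plan; section 8.5.3 leaves stopping to DSMB judgement and sets no threshold. If the table is wrong, an interim statistic between 2.51 and 2.96 has two contradictory readings. A DSMB biostatistician who runs the cited program at 50% will not obtain the protocol's own critical value.

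**Working it through.** **Inputs (all from section 8.5.2).** Two-sided alpha 0.05; O'Brien-Fleming-type Lan-DeMets spending; looks at t = 0.5 and t = 1.

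**Spending function.** With 0.025 on each side, the cumulative two-sided alpha is

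α*(t) = 2 × [2 − 2Φ(z/√t)], where z = Φ⁻¹(1 − 0.05/4) = 2.2414.

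- t = 1/3: 0.00021
- t = 1/2: z/√t = 3.170, so α* = 0.00305
- t = 2/3: z/√t = 2.745, so α* = 0.01210
- t = 1: 0.05000

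The printed interim figure of 0.01210 is reached at t = 0.667, not at 0.50.

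**Boundaries.** These are solved look by look, by numerical integration of the joint normal density, so that the cumulative crossing probability equals α*(t).

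| Plan | Look | z | Per-side alpha | Cumulative alpha |
|---|---|---|---|---|
| Stated: 1/2, 1 | 1 | 2.963 | 0.00153 | 0.00305 |
| | 2 | 1.969 | 0.02450 | 0.05000 |
| Three looks: 1/3, 2/3, 1 | 1 | 3.710 | 0.00010 | 0.00021 |
| | 2 | 2.511 | 0.00601 | 0.01210 |
| | 3 | 1.993 | 0.02313 | 0.05000 |
| Two looks: 2/3, 1 | 1 | 2.509 | 0.00605 | 0.01210 |
| | 2 | 1.993 | 0.02314 | 0.05000 |

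The stated plan does not reproduce Table 11. Looks 2 and 3 of the three-look plan reproduce all six printed figures. The two-look plan at 2/3 and 1 comes close but misses both per-side alphas in the fifth decimal.

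**Other readings at t = (0.5, 1).** None gives 2.51 and 1.99:

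- the spending function applied once to the full 0.05: 2.772, 1.979
- classic O'Brien-Fleming without spending: 2.797, 1.977
- Pocock-type spending: 2.157, 2.201
- power spending with exponent 2: 2.498, 2.018 (interim cumulative 0.01250)
- linear spending: 2.241, 2.125

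**A check that needs no spending function.** At a true first look, cumulative two-sided alpha is exactly twice the per-side alpha. Here 2 × 0.00601 = 0.01202, but the table prints 0.01210. The excess of 0.00008 is too large for rounding and is what an earlier, omitted look would leave.

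**Consequence of using the printed bounds at the stated looks.**

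- Interim: 2 × [1 − Φ(2.51)] = 0.0121, against 0.00305 allowed; 0.0121 / 0.00305 ≈ 4.0.
- Overall two-sided error of ±2.51 at t = 0.5 followed by ±1.99 at t = 1: 0.0526. With the unrounded 2.5114 and 1.9930 it is 0.0522, so rounding accounts for only a small part of the excess.
- Final bound that restores 0.05 if 2.51 is kept at t = 0.5: 2.016, with per-side alpha 0.0219.

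**The case against.** The arithmetic is not in dispute; the practical weight is. Crossing the bound stops nothing: it leads to sponsor notification and a DSMB report. The DSMB receives the interim safety results whether or not a bound is crossed, meets at least annually and can be called at any time. The printed interim value errs on the cautious side, since it flags a difference in adverse events sooner than 2.96 would. No efficacy hypothesis and no sample-size figure depends on Table 11. The overall excess is about 0.0026, and the final bound moves by only 0.02. Because section 8.5.2 names the software, a rerun at the actual information fraction would give correct values.

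All of this stands as a limit on the harm. It does not remove the error, because the text makes Table 11 itself the source of the critical value, so a rerun would contradict the protocol. A sensitive safety bound is a legitimate choice, but the protocol has not declared one; it says O'Brien-Fleming at 50%.

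It is also fair that a carry-over from a three-look table is an inference. The protocol mentions no such plan. The match in six figures and the 0.01202 versus 0.01210 discrepancy make it the best explanation, but the finding does not depend on it.

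**Conclusion.** The concern holds. Table 11 is wrong for the design that section 8.5.2 states. The interim bound should be ±2.963 rather than ±2.51, with 0.0031 rather than 0.0121 spent. The final bound should be ±1.969 rather than ±1.99. As printed, the overall two-sided error is 0.0526 in each of the two populations, taken separately. The substantive error is at the interim; the final bound and the overall level are only slightly off.

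The result assumes information fractions of exactly 0.5 and 1, as the table labels them, and the usual two-sided form of the spending function with 0.025 per side. That form is the one that reproduces the printed digits at 2/3 and 1 in a three-look plan.

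**What to change.** Choose one of two routes before any interim safety data are seen, since choosing between 2.51 and 2.96 afterwards would not be credible.

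1. **Keep the stated method.** Replace the interim row with ±2.96, 0.00153, cumulative 0.00305, and the final row with ±1.97, 0.0245, cumulative 0.0500. This makes the interim flag harder to reach.
2. **Keep 2.51 as a deliberately sensitive safety bound.** Remove the O'Brien-Fleming label, state the rule actually used, and set the final bound to ±2.02 (2.016 before rounding). The interim alphas become about 0.00604 per side and 0.0121 cumulative. The final per-side alpha becomes about 0.0219, with cumulative 0.0500. This makes the final bound slightly stricter.

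The choice belongs to the sponsor and the DSMB. Either route is an edit to one table and, for the second, its note. The alpha columns must be changed along with the bounds. Neither route affects the sample size or the efficacy analyses.
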